#### 1.4.3 Discussion

In the context of the available clinical and preclinical information of BI 1358894, the above mentioned risk mitigation activities to minimise the risk of pregnancy during the trial and the anticipated benefit of BI 1358894 in patients, the risk of participation of a population of healthy individuals is considered acceptable.

Yasmin® has been used extensively for many years and is generally well tolerated. The intake of combined oral contraceptives is associated with an increased risk of serious side effects such as cardiovascular diseases (myocardial infarction, cerebrovascular events, venous

c41232811-04 Trial Protocol

ial Protocol Page 25 of 84

Proprietary confidential information © 2023 Boehringer Ingelheim International GmbH or one or more of its affiliated companies

thromboembolism) and tumours. With a duration of treatment of only 3 months and the mitigation strategies planned the risks are considered acceptable.

c41232811-04 Trial Protocol Page 26 of 84

Proprietary confidential information © 2023 Boehringer Ingelheim International GmbH or one or more of its affiliated companies

## 2. TRIAL OBJECTIVES AND ENDPOINTS

## 2.1 MAIN OBJECTIVES, PRIMARY AND SECONDARY ENDPOINTS

## 2.1.1 Main objective

The main objective of this trial is to investigate the effect of multiple oral doses of BI 1358894 on pharmacokinetics of ethinylestradiol (EE) and drospirenone (DRSP) (Yasmin®).

[figure not shown]
## 2.1.2 Primary endpoints

The following pharmacokinetic parameters will be determined for ethinylestradiol and drospirenone:

- AUC $_{\tau,ss}$  (area under the concentration-time curve of the analyte in plasma at steady state over the uniform dosing interval  $\tau$ ),
- $C_{max,ss}$  (maximum measured concentration of the analyte in plasma at steady state over the uniform dosing interval  $\tau$ )

## 2.1.3 Secondary endpoint

•  $C_{min,ss}$  (minimum measured concentration of the analyte in plasma at steady state over the uniform dosing interval  $\tau$ )

c41232811-04 Trial Protocol

Page 27 of 84

Proprietary confidential information © 2023 Boehringer Ingelheim International GmbH or one or more of its affiliated companies

2.2.2.3 Safety and tolerability

Safety and tolerability of BI 1358894 will be assessed based on:

- Adverse events (including clinically relevant findings from the physical examination)
- Safety laboratory tests
- 12-lead ECG
- Vital signs (blood pressure, pulse rate)
- Suicidality assessment (C-SSRS)

Proprietary confidential information © 2023 Boehringer Ingelheim International GmbH or one or more of its affiliated companies

## 3. DESCRIPTION OF DESIGN AND TRIAL POPULATION

#### 3.1 OVERALL TRIAL DESIGN

The trial will be performed as a non-randomised, open-label, two-period, fixed sequence trial with run-in period in healthy female subjects in order to compare the test treatment (T) to the reference treatment (R).

Reference (R): one tablet of Yasmin® q.d. after a continental breakfast on Days 1-21 in Period 1.

Test (T): one tablet of Yasmin® q.d.  $\pm$  one tablet of BI 1358894 25 mg q.d.  $\pm$  two tablets of BI 1358894 50 mg q.d. after a continental breakfast on Days 1-21 in Period 2.

[figure not shown]
The Reference Treatment will always be followed by the Test Treatment in a fixed sequence. There will be no wash-out period between the treatments.

All subjects will undergo a run-in period that starts between Day -56 and Day -28. In this period, the subjects will take one tablet of Yasmin® daily until Day -8.

In the last 7 days of each treatment period (i.e., Day 22 to Day 28) and the run-in period (i.e. Day -7 to Day -1) no treatment will be given in order to induce bleeding.

For details, refer to Section 4.1.

An overview of all relevant trial activities is provided in the Flow Chart. For visit schedule and details of trial procedures at selected visits, refer to Section 6.1 and 6.2, respectively.

Abbreviation: R=Reference Treatment (Yasmin®); T=Test Treatment (Yasmin® and BI 1358894)

Figure 3.1: 1 Trial design

#### 3.2 DISCUSSION OF TRIAL DESIGN

For this DDI-trial, a fixed-sequence design was chosen to ensure that pharmacokinetic parameters of the respective investigational drugs would be determined in all subjects at approximately the same time point of the menstrual cycle. In this regard BI 1358894 is

BI Trial No.: 1402-0019

c41232811-04 Trial Protocol Page 29 of 84

Proprietary confidential information © 2023 Boehringer Ingelheim International GmbH or one or more of its affiliated companies

considered the offender drug and the COC the victim drug. The design of the trial allows each subject to serve as her own control, the comparison between treatments is based on an intra-subject comparison, thus removing inter-subject variability from the comparison between treatments [R94-1529].

The fixed-sequence design is not expected to lead to systematic errors in the estimation of the treatment effects since non-specific time-effects are unlikely to happen due to the short trial duration.

The open-label treatment is not expected to bias results since the primary endpoints are derived from measurement of plasma concentrations of the analyte.

The PD biomarkers will be measured on day 21 of both periods for exploratory reasons.

For the victim drug (EE + DRSP) the dosing duration (21 days dosing followed by 7 days of no treatment) is long enough to reliably achieve steady-state drug exposure in both treatment periods.

To exclude possible interaction with any preceding oral contraceptive regime and to minimize the influence of adaptation to a newly administered oral contraceptive, all participants will undergo a run-in period of at least 28 days (including treatment with Yasmin® for at least 21 days) before the beginning of the first study period.

#### 3.3 SELECTION OF TRIAL POPULATION

It is planned that approximately 32 healthy female subjects will enter the trial and start period 1. They will be recruited from the volunteers pool of the trial site.

A log of all subjects enrolled into the trial (i.e. who have signed informed consent) will be maintained in the ISF, irrespective of whether they have been treated with investigational drug or not.

#### 3.3.1 Main diagnosis for trial entry

The trial will be performed in healthy female subjects.

Please refer to Section 8.3.1 (Source Documents) for the documentation requirements pertaining to the in- and exclusion criteria.

#### 3.3.2 Inclusion criteria

Subjects will only be included in the trial if they meet the following criteria:

Boehringer Ingelheim 19 Oct 2023 BI Trial No.: 1402-0019

Proprietary confidential information © 2023 Boehringer Ingelheim International GmbH or one or more of its affiliated companies

- 1. Healthy premenopausal female subjects according to the assessment of the investigator, as based on a complete medical history including a physical and gynaecological examination, vital signs (BP, PR), 12-lead ECG, and clinical laboratory tests
- 2. Age of 18 to 35 years (inclusive)
- 3. BMI of 18.5 to  $29.9 \text{ kg/m}^2$  (inclusive)
- 4. Signed and dated written informed consent in accordance with ICH-GCP and local legislation prior to admission to the trial
- 5. Female subject who meet any of the following criteria for a highly effective contraception from at least 30 days before the first administration of trial medication until 30 days after trial completion:
  - Use of an oral hormonal contraception method in combination with a barrier contraception method and willing to stop the hormonal method and to continue using the barrier method plus Yasmin® for the duration of the trial
  - Use of non-hormonal intrauterine device (IUD)
  - Sexually abstinent
  - Female subject who underwent tubal ligation
  - A vasectomised sexual partner who received medical assessment of the surgical success (documented absence of sperm) and provided that partner is the sole sexual partner of the trial participant

#### 3.3.3 Exclusion criteria

Subjects will not be allowed to participate, if any of the following general criteria apply:

- 1. Any finding in the medical examination (including BP, PR or ECG) deviating from normal and assessed as clinically relevant by the investigator (e.g. pronounced varicosis, thrombophlebitis, and evidence of peripheral circulatory disturbances)
- 2. Repeated measurement of systolic blood pressure outside the range of 90 to 140 mmHg, diastolic blood pressure outside the range of 50 to 90 mmHg, or pulse rate outside the range of 50 to 90 bpm
- 3. Any laboratory value outside the reference range that the investigator considers to be of clinical relevance
- 4. Any evidence of a concomitant disease assessed as clinically relevant by the investigator
- 5. Gastrointestinal, hepatic, renal, respiratory, cardiovascular, metabolic, immunological or hormonal disorders
- 6. Cholecystectomy or other surgery of the gastrointestinal tract that could interfere with the pharmacokinetics of the trial medication (except appendectomy or simple hernia repair)

c41232811-04 Trial Protocol Page 31 of 84

Proprietary confidential information © 2023 Boehringer Ingelheim International GmbH or one or more of its affiliated companies

- 7. Diseases of the central nervous system (including but not limited to any kind of seizures or stroke), and other relevant neurological or psychiatric disorders
- 8. History of relevant orthostatic hypotension, fainting spells, or blackouts
- 9. Relevant chronic or acute infections
- 10. Any documented active or suspected malignancy or history of malignancy within 5 years prior to screening, except appropriately treated basal cell carcinoma of the skin
- 11. History of relevant allergy or hypersensitivity (including allergy to the trial medication or its excipients)
- 12. Use of drugs within 30 days prior to treatment allocation that might reasonably influence the results of the trial (including drugs that cause QT/QTc interval prolongation)
- 13. Intake of an investigational drug in another clinical trial within 60 days prior to treatment allocation, or concurrent participation in another clinical trial in which investigational drug is administered
- 14. Smoker (former smokers must have stopped smoking at least 6 months before screening) or positive cotinine test at screening
- 15. Alcohol abuse (consumption of more than 12 g per day)
- 16. Drug abuse or positive drug screening
- 17. Blood donation of more than 100 mL within 30 days prior to treatment allocation or intended blood donation during the trial
- 18. Intention to perform excessive physical activities within one week prior to treatment allocation or during the trial
- 19. Inability to comply with the dietary regimen of the trial site
- 20. A marked prolongation of QT/QTcF interval (such as QTcF intervals that are repeatedly greater than 470 ms in females) or any other relevant ECG finding at screening
- 21. A history of additional risk factors for *Torsade de Pointes* (such as heart failure, hypokalaemia, or family history of Long QT Syndrome)
- 22. Subject is assessed as unsuitable for inclusion by the investigator, for instance, because the subject is not considered able to understand and comply with study requirements, or has a condition that would not allow safe participation in the study
- 23. Lactation or pregnancy within the last 6 months, or plans to become pregnant during the trial or within 30 days after trial completion
- 24. Positive pregnancy test

In addition, the following trial-specific exclusion criteria apply:

Boehringer Ingelheim 19 Oct 2023 BI Trial No.: 1402-0019

c41232811-04 Trial Protocol Page 32 of 84

Proprietary confidential information © 2023 Boehringer Ingelheim International GmbH or one or more of its affiliated companies

25. Use of drugs which may interfere with Yasmin® in accordance to the SmPC within 30 days prior to treatment allocation (including moderate and strong CYP3A4 inhibitors, CYP3A4 inducers, St. John's wort, etc.)

- 26. Use of other hormone-containing methods of contraception except Yasmin® per trial protocol, e.g. hormone-containing intrauterine device, depot injection or contraceptive implants. Subjects taking oral contraceptives other than Yasmin® will be allowed to participate as long as they agree to stop their current oral contraceptive and accept taking Yasmin® for the duration of the trial.
- 27. History of confirmed venous thromboembolism, family history of venous thromboembolism, and other known risk factors for venous thromboembolism
- 28. History of malignancy within 5 years (except appropriately treated basal cell carcinoma of the skin). Any history of breast cancer will lead to exclusion.
- 29. History or evidence of arterial thrombotic or embolic processes, conditions which predispose to them (such as disorders of the clotting processes, valvular heart disease, atrial fibrillation, autoimmune diseases, dyslipidaemia, etc.)
- 30. History of migraine in the past 5 years
- 31. History of relevant liver diseases (e.g. disturbances of liver function, jaundice or persistent itching during a previous pregnancy, Dubin-Johnson syndrome, Rotor syndrome, or previous or existing liver tumours)
- 32. History of bipolar mood disorder, bulimia or anorexia
- 33. History of suicidal ideation of type 2 to 5 on the C-SSRS in the past 12 months (i.e. active suicidal thought, active suicidal thought with method, active suicidal thought with intent but without specific plan, or active suicidal thought with plan and intent) or any suicide attempt in the past 24 months (i.e. actual attempt, interrupted attempt) prior to screening
- 34. History of major depressive disorder
- 35. Clinically relevant finding in the gynaecological anamnesis, gynaecological examination which in the opinion of the gynaecologist oppose the prescription of Yasmin®
- 36. Clinically relevant result of the cervical smear

For restrictions of the trial, refer to Section 4.2.2.

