- 7. The intake of Yasmin® starts depending on the subjects' actual menstruation cycle and at least -28 days before Day 1 of first treatment period. In the run-in period, the subjects will take one tablet of COC daily until Day -8. On Day 7 to Day -1 no COC tablets will be given in order to induce withdrawal bleeding. Self-administration in the morning with no requirement of fasting. Self-administration to be documented in the diary. A negative urine pregnancy test should be performed at the site 1 to 7 days before start of the run-in. Details are outlined in Section 4.1.4
- 8. Urine pregnancy test. Additional urine drug screening on day 20 of each period.
- 9. Blood collection takes place within 10 minutes before dosing.
- 10. Suicidality assessment using the Columbia-Suicidal Severity Rating Scale (C-SSRS): 'Screening/Baseline' version at Visit 1, and 'since last visit' version at other visits.
- 11. Measurement of exploratory pharmacodynamic parameters: estradiol, luteinizing hormone (LH), follicle stimulating hormone (FSH), and progesterone. The samples will be taken in duplicate.
- 12. Dosing at the trial site after a continental breakfast (for details see Section 4.1.4).

c41232811-04 Trial Protocol

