#### 3.3.4.1 Withdrawal from trial treatment

An individual subject will be withdrawn from trial treatment if:

- 1. The subject wants to withdraw from trial treatment. The subject will be asked to explain the reasons but has the right to refuse to answer
- 2. The subject has repeatedly shown to be non-compliant with important trial procedures and, in the opinion of both, the investigator and sponsor representative, the safety of the subject cannot be guaranteed as she is not willing or able to adhere to the trial requirements in the future. For details regarding missed visits see Section 6.1.
- 3. The subject needs to take concomitant medication that interferes with the investigational medicinal product or other trial treatment
- 4. The subject can no longer receive trial treatment for medical reasons (such as pregnancy, surgery, adverse events (AEs), or diseases)
- 5. The subject has an elevation of AST and/or ALT ≥3-fold ULN and an elevation of total bilirubin ≥2-fold ULN (measured in the same blood sample) and/or needs to be followed up according to the DILI checklist provided in the ISF
- 6. Suicidal ideation (type 2-5) or any suicidal behaviour based on C-SSRS questionnaires during the trial
- 7. The subject experiences a drug-related adverse event of severe intensity or a serious adverse event
- 8. In addition to these criteria, the investigator may discontinue subjects at any time based on his or her clinical judgment.
- 9. If it is known that a subject becomes pregnant during the trial, administration of the trial medication is to be stopped immediately, and the subject is to be removed from the trial. The subject is to be followed until she has given birth or until the end of the pregnancy. The subject's data are to be collected until the end of the trial (last visit of last subject) and reported in the CTR. For reporting of pregnancy and associated events, refer to Section 5.2.6.2.3.
- 10. If new efficacy or safety information becomes available, Boehringer Ingelheim will review the benefit-risk-assessment and, if needed, pause or discontinue the

c41232811-04 Trial Protocol

Page 34 of 84

Proprietary confidential information © 2023 Boehringer Ingelheim International GmbH or one or more of its affiliated companies

trial treatment for all subjects or take any other appropriate action to guarantee the safety of the trial subjects.

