#### 5.2.5 Other safety parameters

#### 5.2.5.1 Suicidality assessment

The C-SSRS is a semi-structured, investigator-rated interview, developed by clinical experts in cooperation with the FDA, assessing both suicidal behaviour and suicidal ideation. It does not give a global score, but provides some categorical and some severity information specifically for behaviour and ideation [R08-1147].

The C-SSRS interview may be administered by a physician or a study nurse with C-SSRS training. It has a typical duration of five minutes, and causes only a low burden on subjects. At a minimum, the interview consists of 2 screening questions related to suicidal ideation and 4 related to suicidal behaviour, and may be expanded to up to 17 items in case of positive responses. Free text entries are allowed.

The C-SSRS has been widely used in large multinational CTs. The C-SSRS will be administered at the screening visit (using the 'screening / baseline' version) with the aim to exclude subjects with active moderate or severe symptomatology within a specified time prior to the screening or baseline visit. The life time history of suicidal ideation and behaviour will also be recorded. See Section 10.1 for the original English C-SSRS. For this trial, the paper version of the respective German translation will be used. After the screening visit, the 'since last visit' version is used for the suicidality assessment at the time points indicated in the Flow Chart.

**Positive** reports are generated for any of the following findings:

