#### Suicidal behavior

- Completed suicide
- Suicide attempt
- Interrupted attempt
- Aborted attempt
- Preparatory actions toward imminent suicidal behaviors.

Negative reports of suicidal ideation are defined as reports when there are no indications of the above, i.e. suicidal ideation of type 1-3.

The investigator is to review positive and negative reports for plausibility and clinical relevance. Doubtful reports may be repeated or reports may be validated by a consulting psychiatrist.

If there is a confirmed positive report of suicidal behaviour or suicidal ideation type 4 or 5 after start of trial, the investigator is to immediately interview the subject during the clinic visit, and/or is to consult a psychiatrist. If the positive report is confirmed, appropriate actions for the subject's safety have to be initiated.

For details regarding AE reporting see section 5.2.6.2.4

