#### 5.2.6.2.4 AE reporting from suicidality assessment

All positive reports from C-SSRS suicidality assessment (see Section 5.2.5.1), i.e. reports of suicidal ideation type 4 or 5 and all reports of suicidal behaviour must be reported as separate SAEs by the investigator.

Negative reports (i.e. suicidal ideation type 1, 2 or 3) can be reported as AEs, at the discretion of the investigator. All negative reports should be reviewed by the Investigator for clinical relevance and determination if an AE report is warranted

BI Trial No.: 1402-0019

Proprietary confidential information © 2023 Boehringer Ingelheim International GmbH or one or more of its affiliated companies

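### Exclusion criterion 33 leaves aborted suicide attempts and preparatory acts 12 to 24 months before screening to case-by-case judgment (minor safety point)

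*Protocol*

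**What the plan says.** Criterion 33 in Protocol Section 3.3.3 has two limbs. The first excludes C-SSRS ideation of types 2 to 5 in the 12 months before screening. The second excludes "or any suicide attempt in the past 24 months (i.e. actual attempt, interrupted attempt) prior to screening".

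Section 5.2.5.1 lists the behaviours that make a C-SSRS report positive. Besides completed suicide, suicide attempt and interrupted attempt, it includes aborted attempts and "Preparatory actions toward imminent suicidal behaviors". Of the screening interview it says: "The life time history of suicidal ideation and behaviour will also be recorded". It adds: "The investigator is to review positive and negative reports for plausibility and clinical relevance".

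During the trial the rules cover all behaviour types. Section 3.3.4.1, item 6, requires withdrawal from treatment for "Suicidal ideation (type 2-5) or any suicidal behaviour based on C-SSRS questionnaires during the trial". Under Section 5.2.6.2.4, "all reports of suicidal behaviour must be reported as separate SAEs by the investigator".

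Flow Chart footnote 10 sets the C-SSRS versions: "Screening/Baseline' version at Visit 1, and 'since last visit' version at other visits".

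**The concern.** The second limb of criterion 33 uses i.e., not e.g., so its list is complete as written and omits aborted attempts and preparatory acts. By the definitions on the C-SSRS form (Section 10.1), an interrupted and an aborted attempt differ in who stopped the act: an outside circumstance or the woman herself. Criterion 33 excludes the first by rule at, say, 18 months before screening and leaves the second to discretion. The documents give no reason for the difference.

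Only subject safety is at stake. These are healthy volunteers with no therapeutic benefit (Section 1.4.1). They would take an investigational drug being developed for psychiatric disorders (Section 1) together with a contraceptive for which depressed mood is among the most common adverse events (Section 1.2.2.3). For part of that risk the sponsor already uses a fixed rule, because any past major depressive disorder excludes (criterion 34).

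**Working it through.** No planned figure needs reproducing here. The check compares the rules and then asks whether any other rule closes the gap.

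**Step 1: behaviour types.** Section 5.2.5.1 lists five suicidal behaviours; without completed suicide, 5 − 1 = 4 remain. The C-SSRS form defines each of the four separately.

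| Behaviour | Excluded by criterion 33 (24 months) | Positive report (5.2.5.1) | Withdrawal on trial (3.3.4.1, item 6) | SAE on trial (5.2.6.2.4) |
|---|---|---|---|---|
| Actual attempt | Yes | Yes | Yes | Yes |
| Interrupted attempt | Yes | Yes | Yes | Yes |
| Aborted attempt | Not named | Yes | Yes | Yes |
| Preparatory acts | Not named | Yes | Yes | Yes |

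Criterion 33 names 2 of 4, which leaves 4 − 2 = 2 outside. A lenient reader might count an aborted attempt as a suicide attempt despite the closed list. Preparatory acts would still fall outside.

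**Step 2: the time window.** In months 0 to 12 before screening, such behaviour would usually come with type 2 to 5 ideation, so the first limb probably excludes most of these women. That is an assumption, as the documents have no data on it. The gap is therefore mainly months 12 to 24.

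**Step 3: other routes to exclusion.** Take a woman with an aborted attempt or preparatory acts in months 12 to 24 and no type 2 to 5 ideation in months 0 to 12.

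- Criterion 33, ideation limb: not met.
- Criterion 33, behaviour limb: not met, because her behaviour is not named.
- Inclusion criterion 1, exclusion criteria 4 and 7, and the investigator's review of C-SSRS reports: these depend on a judgment of health or clinical relevance.
- Criterion 22: also judgment. It applies if she is considered unsuitable, for instance if she cannot comply "or has a condition that would not allow safe participation in the study".
- Criteria 32 and 34: these need a history of bipolar disorder, an eating disorder or major depressive disorder.

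None of these excludes her by rule on the behaviour itself.

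**Step 4: later checks.** Every C-SSRS after Visit 1 is the since-last-visit version, so it does not reach back before screening. As far as the Flow Chart can be read, seven are scheduled: Period 2 Days 1, 7, 14, 20 and 22, the Day 23–28 call, and end of study. None falls in the run-in or Period 1. Timing of the first, at Period 2 Day 1 before dosing:

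- The run-in starts between Day −56 and Day −28 (Section 3.1), there is no Day 0 (Section 4.1.4), and Period 1 lasts 28 days (Section 6.2.2).
- From the start of the run-in: 28 + 28 = 56 days to 56 + 28 = 84 days.
- From the earliest screening day, Day −91 (Flow Chart): 91 + 28 = 119 days.

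These checks detect new ideation or behaviour. They do not apply a rule to the earlier history, so that has to be done at entry.

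**The case against.** The strongest reply is that leaving this case to judgment is defensible. The screening interview must ask about every behaviour type, and lifetime behaviour is recorded. The investigator reviews positive reports and may have them validated by a psychiatrist. Relevant criteria are re-checked before the run-in (Section 4.1.3). What remains is a woman with a remote event, no recent type 2 to 5 ideation and no excluding diagnosis, whom a physician has reviewed and found suitable. Section 5.2.5.1 describes the screening aim in terms of active symptoms, and her history is not clearly active, so no stated aim is missed. Entry and on-trial rules may also legitimately differ. The ideation thresholds already vary by purpose: types 2 to 5 for entry and withdrawal, types 4 and 5 for a positive report.

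All of this stands, and it makes the point a design choice and not an error. It does not supply a rule where criterion 33 has none.

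A second reply is that the C-SSRS timing figures describe monitoring, which rewording criterion 33 would not change. That is correct. They show only that later visits do not make up for the entry rule. Monitoring is also fuller than the C-SSRS schedule alone suggests: Period 1 doses are given at the site, adverse events are asked about on each dosing day, specific questions follow where necessary, and the investigator may discontinue a subject at any time. A C-SSRS also precedes the first BI 1358894 dose.

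Third, the public text omits the BI 1358894 profile and its rows in the risk table. Any risk or mitigation described there cannot be weighed, and nothing visible shows that these two remote behaviours raise risk in this trial. That limits the weight of the point.

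**Conclusion.** The point holds as a minor, optional safety improvement. Criterion 33 excludes by rule on 2 of the 4 non-fatal behaviour types. The other 2, in months 12 to 24 before screening and without type 2 to 5 ideation in the past 12 months, are left to judgment or to a separate diagnosis. This rests on reading the parenthesis as a closed list, which is its plain meaning.

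Confidence is high on the wording. The size of any safety consequence is unknown: the documents give no frequency, and that few women would be affected is an assumption. No endpoint, estimate, analysis or sample size changes. According to SAP Section 6.1, 28 women were treated in the run-in and none received BI 1358894, so the realised effect on exposure to that drug was nil. The practical value lies in any restart or reuse of the criterion.

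**What to change.** In criterion 33, change the second limb from suicide attempt to any suicidal behaviour, keep the 24-month look-back, and let the parenthesis list actual attempt, interrupted attempt, aborted attempt, and preparatory acts or behaviour. The entry rule then covers the same behaviours as withdrawal item 6.

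The cost is one line of text. No new data are needed: the screening form in Section 10.1 already asks about all four types, with lifetime and recent-years answers. The downside is an occasional extra screen failure.
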